1.2 Overview of Clinical Studies

Two previous studies of glutathione (oral or oral with inhaled) in people with CF have provided encouraging results, demonstrating improvements in weight and other clinical parameters.

Study 1: Visca, et al. published a placebo-controlled, randomized, double blind study evaluating the impact of oral glutathione on growth parameters in an Italian pediatric CF cohort [6]. In this study, 44 children ages 18 months to 10 years, receiving pancreatic enzyme replacement therapy (PERT), were randomized to receive either placebo or oral glutathione daily for 6 months. Patients received 65mg/kg/day of oral GSH or placebo of calcium citrate at 65mg/kg/day. This dose was divided into three doses with one being given at each meal. The subjects receiving oral glutathione gained an average of 0.67 weight-for-age z-score over the course of the 6 month trial while the placebo group showed an average increase in weight z-score of 0.10. The overall difference between the two groups in the 6-month change from baseline was statistically significant with a p value of < 0.0001. Similarly, the overall difference between groups in the 6-month change from baseline for BMI-for age z-score was statistically significant (glutathione mean change: 0.60, placebo mean change: 0.22, $p < 0.0001$) (See Figure A below) [6].

Noticably, there was a difference between the two treatment groups in both weight-for-age z-score at baseline (-0.84 in the treated group versus -0.54 in the placebo group) and BMI-for-age z-score at baseline (-0.76 in the treated group versus -0.57 in the placebo group). Although these differences were not statistically significant, the treated group had greater opportunity for improvement than the group treated with placebo.

Secondary outcome measures in this study included blood alanine aminotransferase (ALT), WBC, Vitamin E, and CRP. Each of these improved significantly in the glutathione treated group compared to placebo (See Table 3 below).

TABLE 3. Results from analysis of the secondary outcomes

Secondary outcome	GSH group 6-mo change, mean (SD)	Placebo group 6-mo change, mean (SD)	P 2-sample t test	95% CI for difference
WBCs	-0.66 (0.69)	0.62 (0.71)	0.0001	-1.7 to -0.9
ALT	-5.1 (3.6)	3.2 (4.1)	0.0001	-10.6 to -6.0
Vitamin E	0.89 (0.5)	-0.75 (0.53)	0.0001	1.3-1.9
CRP	-2.6 (3.1)	2.6 (2.9)	0.0001	-7.0 to -3.4

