8 STUDY TREATMENTS

8.1 Method of Assigning Subjects to Treatment Groups

Randomization will occur centrally using a web based randomization system linked to the electronic data capture (EDC) system. Eligible subjects will be randomly assigned to receive study drug (GSH or placebo) in equal allocation. Study personnel at the investigative site will

use the Medidata[®] Rave[®] and Balance[®] systems to randomize each subject. An adaptive randomization scheme (dynamic allocation based on minimization [29]) will be employed with the goal of ensuring equal representation in each study arm and strata. Subject randomization will be stratified by sex, baseline age (< 6 years, ≥ 6 years), baseline weight-for-age z-score (< -0.52, ≥ -0.52, i.e., the 30th percentile) and historical fecal elastase (<200 µg/g, ≥200 µg/g, unavailable). The dynamic allocation algorithm seeks to optimize randomization balance by minimizing a weighted average of the marginal imbalance [30] of treatment allocation for each factor and for the study overall. A random element is added to the otherwise deterministic minimization algorithm to reduce allocation predictability by using a biased coin (32) to include a chance of allocation to a treatment arm other than the arm that optimizes balance.

Only authorized site personnel are given access to the randomization module. Authorized site personnel will enter subject eligibility information and whether or not the subject signed informed consent. The system will verify that the subject is eligible and has provided signed informed consent; the system will then provide the appropriate authorized site personnel with a randomization assignment for the subject that matches a specific treatment.

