15.3 Analysis of Primary Endpoint

Based on evidence from prior studies, it is hypothesized that six months of oral GSH will be associated with an improved weight-for-age z-score as compared to six months of oral placebo. Therefore the null hypothesis is that there is no difference between treatment groups in the 6 month change in weight-for-age z-score.

The primary endpoint is the difference between the GSH and placebo groups in the change in weight-for-age z-score from Visit 2 to Visit 4 (Week 24). The difference between treatment groups will be estimated using a linear mixed effects model which will incorporate Visit 3 (Week 12) weight-for-age z-score measurements. The model will adjust for randomization strata and assume, if estimable, an unstructured covariance structure. Least squares means at each visit and the estimated treatment effect and corresponding 95% confidence intervals and p-values will be reported from the model. The p-value will be evaluated against a two-sided 0.05 level of significance. Weight-for-age z-scores will be calculated using CDC reference equations [32]. Graphical displays will be used to show both unadjusted and adjusted mean changes in weight-for-age z-score between visits for the two treatment groups.

Sensitivity analyses of the primary endpoint will include:

- Performing the primary efficacy analysis on the per-protocol population.

- Performing the primary efficacy analysis on the sub population of subjects determined to be pancreatic insufficient (defined as documented fecal elastase < 200 µg/g).
- Missing data methods.

Missing data sensitivity analyses of the primary endpoint will include the least favorable treatment arm imputation method, which imputes missing values with the mean change from the treatment arm with the worst change in the observed case analysis. Further details regarding missing data methods will be provided in the SAP.

Additional sensitivity analyses of the primary endpoint may be performed to adjust for potential baseline confounders.

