15.9 Sample Size

The primary endpoint is the difference between treatment groups of the change in weight-for-age z-score from Visit 2 to Visit 4 (Week 24). Data from prior studies of similar populations and durations are available to estimate sample size and power for the study including a randomized, placebo-controlled trial of oral GSH in Italian children chronically taking pancreatic enzymes, as well as a factorial randomized trial comparing antipseudomonal regimens in US children with newly acquired *Pseudomonas aeruginosa* infection. These studies suggest a standard deviation of the change in weight-for-age z-score ranging from 0.20 to 0.29. A query of CF registry data of a similar population found the standard deviation of the 6-month change in weight-for-age z-score to be higher (0.37). A previous study of oral GSH in children, conducted in Italy, found the weight-for-age z-score difference between the GSH arm and the placebo arm after 6 months of therapy to be 0.34. The following table provides example weight changes in kilograms over a 6 month period for certain patient age and sex combinations, as well as how those gains translate into changes in weight-for-age z-score.

Subject Age and Sex at Baseline	Weight Baseline (kg)	Weight Visit 4 (kg)	6-month change (kg)	Weight at baseline (z-score)	Weight at Visit 4 (z-score)	6 month change (z-score)
9-year old boy	25	28	3	-0.87	-0.46	0.42
7-year old girl	19	20.75	1.75	-1.27	-1	0.27
3-year old boy	14	15.25	1.25	-0.21	0.01	0.22
4-year old girl	15	17.5	2.5	-0.4	0.28	0.68

The figure below displays a range of detectable treatment effect sizes and resulting sample sizes for 3 standard deviations (SD = 0.2, 0.3 and 0.4) Assuming a conservative standard deviation of 0.4, a total sample size of 54 provides 90% power to detect a treatment effect of 0.36 or greater. It is anticipated from prior CF trials conducted through the TDNCC that the attrition rate will be less than 10% for a study of this duration, thus it is reasonable to expect that a total sample size of 60 will enable at least 54 subjects to complete the trial.

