3.4 Primary Endpoint

Weight-for-age z-score, the primary outcome measure, will be calculated using CDC reference equations based on age, sex, and weight. The number and percent of expected and observed measurements of weight-for-age z-score across visits will be tabulated by treatment group, along with reasons for missingness and the number and percent of participants with both baseline and end of study measurement.

The primary endpoint is the difference between the GSH and placebo groups in the change in weight-for-age z-score from Visit 2 (Baseline) to Visit 4 (Week 24). The difference between treatment groups will be estimated using a linear mixed effects model which will incorporate Visit 3 (Week 12) weight-for-age z-score measurements. The model will adjust for randomization strata, i.e., sex (male, female), baseline age (< 6 years, ≥ 6 years), baseline weight-for-age z-score category (< -0.52, ≥ -0.52), and historical fecal elastase (<200 µg/g, ≥200 µg/g, unavailable) and assume, if estimable, an unstructured covariance structure. Least squares mean changes at each visit and the estimated treatment differences with corresponding 95% confidence intervals from the model will be presented. The model-based p-value for the Visit 4 (Week 24) treatment difference will be evaluated against a two-sided 0.05 level of significance. Graphical displays will be used to show unadjusted mean changes in weight-for-age z-score across visits for the two treatment groups.

Sensitivity analyses of the primary endpoint will include:

- Performing the primary efficacy analysis on the per-protocol population.
- Performing the primary efficacy analysis on the sub population of subjects determined to be pancreatic insufficient (defined as fecal elastase < 200 µg/g).
- Least favorable treatment group imputation, which imputes missing values with the mean change from the treatment group with the worst change in the observed case analysis,

conservatively assuming that any participants who dropped out of the study had a less than favorable result.

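### Primary mixed model: baseline weight z-score is only a two-level covariate and the response is undefined, so the strata adjustment may not reach the 24-week change

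*SAP*

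**What the plan says.** Protocol 15.3 estimates the treatment difference in 24-week change from a linear mixed model that also uses the Week 12 value. On adjustment it says: "The model will adjust for randomization strata and assume, if estimable, an unstructured covariance structure". SAP 3.4 repeats this and lists the strata as sex, age group, fecal elastase group and "baseline weight-for-age z-score category (< -0.52, ≥ -0.52"). The protocol synopsis gives the same cut.

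Three things are not stated in either document:

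- whether the response vector is the z-score at Visits 2, 3 and 4, or the change at Visits 3 and 4;
- whether the strata interact with visit;
- any continuous baseline covariate, or any constraint that the arms share one baseline mean.

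The output wording does not settle the first. Protocol 15.3 reports model means by visit, which suggests z-scores as the response. SAP 3.4 reports model mean changes, which fits either. Protocol 15.3 also allows optional sensitivity analyses for baseline confounders; the SAP 3.4 list of sensitivity analyses has none.

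**The concern.** Two statisticians could follow SAP 3.4 faithfully, fit different models and report different primary estimates. In one of those models the promised strata adjustment does nothing, or almost nothing, to the quantity being tested.

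Baseline weight is also the covariate that the protocol worries about most. Protocol 1.2 reports, for the earlier Italian trial, "weight-for-age z-score at baseline (-0.84 in the treated group versus -0.54 in the placebo group"), and notes that the treated arm had more room to gain. Protocol 2 names this imbalance as a reason why that trial was inconclusive. A continuous Visit 2 value is collected from every child, but as a covariate only its side of one cut is used.

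The same gap carries over to the models that SAP 3.8, 3.9 and 3.11 describe as analogous to the primary one: eight anthropometric endpoints, six spirometry endpoints and fecal calprotectin.

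**Working it through.** **Inputs from the documents.** The test "will be evaluated against a two-sided 0.05 level of significance" (SAP 3.4). From Protocol 15.9: "Assuming a conservative standard deviation of 0.4", and "a total sample size of 54 provides 90% power to detect a treatment effect of 0.36 or greater". Allocation is 1:1: "Eligible subjects will be randomly assigned to receive study drug (GSH or placebo) in equal allocation" (Protocol 8.1). Attrition: "the attrition rate will be less than 10% for a study of this duration" (Protocol 15.9). Eligibility is the 10th to 50th weight percentile at screening (Protocol 6.2), so z is about -1.28 to 0.

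**Assumptions, not in the documents.** Baseline values are spread evenly over those percentiles. The correlation r between baseline z-score and 24-week change lies between 0 and -0.5.

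**1. The plan's own figure.** n per arm = 2(1.960 + 1.282)² × 0.4² / 0.36² = 2 × 10.51 × 0.16 / 0.1296 = 25.9, so 26 per arm. With the t distribution, 26 per arm gives 88.9% power and 27 per arm gives 90.1%. The stated 54 is reproduced, and 54 / 0.9 = 60. This is an unadjusted comparison, so the sample size does not depend on the form of the covariates.

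**2. Z-scores at Visits 2 to 4, strata as main effects.** Write Y(i,v) = μ(v) + τ(v)A(i) + S(i)'β + e(i,v). Then

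Y(i,4) − Y(i,2) = [μ(4) − μ(2)] + [τ(4) − τ(2)]A(i) + [e(i,4) − e(i,2)].

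The term S(i)'β has gone. With complete data the estimate of τ(4) − τ(2) is the raw difference in mean change, whatever the covariance matrix. In one simulated data set it was 0.2873 with and without strata under three arbitrary covariance matrices, and 0.2227 once strata-by-visit terms were added.

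**3. Simulation.** There were 40 trials of 60 children per scenario, with unstructured covariance fitted by REML. The baseline slope was -0.35, so r is about -0.35 × 0.3545 / 0.4 = -0.31. Allocation was simple 1:1. Shift is the largest absolute change in the estimate against the model without strata.

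| Model | Mean SE, complete | Shift, complete | Mean SE, 10% dropout | Shift, 10% dropout |
|---|---|---|---|---|
| Z-scores, no strata | 0.1031 | – | 0.1043 | – |
| Z-scores, strata main effects | 0.1031 | 1e-14 | 0.1044 | 0.022 |
| Z-scores, strata by visit | 0.1015 | 0.152 | 0.1057 | 0.118 |
| Changes, strata main effects | 0.1003 | 0.106 | 0.1040 | 0.080 |
| Changes, strata by visit | 0.1015 | 0.152 | 0.1059 | 0.126 |
| Changes, strata and continuous baseline by visit | 0.1015 | 0.145 | 0.1050 | 0.140 |

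With dropout, the shift from strata main effects had SD 0.008. The simulation did not use minimization, which balances the strata, so the larger shifts should be smaller in the actual trial.

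**4. What the cut keeps.** Baseline SD is 0.3545, and 50.4% of children fall below -0.52. The two-level category explains 72.6% of baseline variance, so about 27% is lost. The SD within a category is 0.186.

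**5. Power at 27 per arm and a difference of 0.36.** Residual SD = 0.4√(1 − 0.726r²) with the category and 0.4√(1 − r²) with the continuous value. At r = -0.5 these are 0.3619 and 0.3464.

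| r | No effective adjustment | Category | Continuous |
|---|---|---|---|
| 0 | 90.1% | 90.1% | 90.1% |
| -0.2 | 90.1% | 90.9% | 91.2% |
| -0.3 | 90.1% | 91.9% | 92.5% |
| -0.5 | 90.1% | 94.8% | 96.3% |

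The loss from dichotomizing is at most 96.3 − 94.8 = 1.5 points. The loss if the adjustment does not reach the change is at most 96.3 − 90.1 = 6.2 points. The residual-SD formula leaves out the degrees of freedom that the covariates use.

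**6. Imbalance left inside balanced categories.** SE of the difference in baseline means = 0.186 × √(2/27) = 0.051. A chance imbalance of one such SE moves the estimate by |r| × (0.4 / 0.3545) × 0.0505: 0.006 at r = -0.1 and 0.029 at r = -0.5, against a target of 0.36.

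**7. Type I error if balanced strata are ignored.** 2[1 − Φ(1.96 / √(1 − R²))] = 0.044, 0.039 and 0.028 for an assumed R² of 5%, 10% and 20%. All are below 0.05.

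**The case against.** The strongest reply is that the design already deals with baseline weight. Minimization balances the z-score category (Protocol 8.1), and adjusting for stratification factors as randomized is a respectable choice. Randomization makes the unadjusted difference in change unbiased. A continuous covariate is then a refinement, and a small one: at r about -0.31 with complete data, the simulated mean SE was 0.1015 with and without it. All of this stands, and it limits the size of the point.

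Three stronger readings are tempting, and the documents do not support them.

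- **That the plan's adjustment has no effect.** This is exact only for z-scores at Visits 2 to 4, main effects only and complete data. Protocol 15.1 lets the SAP modify the plan, and the SAP's mean-change wording fits change as the response equally well. Nothing rules out strata-by-visit terms. With Visit 2 in the response, the continuous baseline is also in the model as an outcome, so the two-level limit applies to the covariate list.
- **That the earlier trial's imbalance could recur unseen, because both arm means lie below -0.52.** Arm means do not place every child below the cut, and -0.54 lies almost on it. With balanced categories, a 0.30 imbalance would be 0.30 / 0.051 = about 5.9 standard errors, which is practically excluded.
- **That the test is invalid.** Ignoring balanced strata makes it conservative.

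The missing confounder analysis breaks no commitment, since Protocol 15.3 made it optional.

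What the reply does not answer is that the primary model is not fully specified, and that a reader cannot tell whether the stated adjustment acts on the primary contrast.

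**Conclusion.** The point holds as a specification gap with a modest cost in precision. SAP 3.4 leaves the response vector open. On one permissible reading the strata adjustment cancels from the primary contrast; on the other it works but discards about 27% of the baseline variance. The expected loss is about 0 to 1.5 power points from dichotomizing, or 0 to 6 if the adjustment does not reach the change. Neither bias nor inflated type I error follows.

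These sizes rest on an assumed correlation of 0 to -0.5, a baseline distribution inferred from the eligibility range, and the planned SD of 0.4. The cancellation itself is algebra and needs none of them. The change is worth making because it is almost free, it fixes which model is primary, and it uses the measurement that the protocol most wanted to control.

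**What to change.** In SAP 3.4, choose one model and write it out before unblinding:

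- **Preferred.** Response: change in weight-for-age z-score at Visits 3 and 4. Fixed effects: arm, visit, arm by visit, continuous Visit 2 z-score, Visit 2 z-score by visit, and the stratification factors (sex, age group, elastase group, and the z-score category if it is kept). Unstructured covariance as now.
- **Alternative, if Visit 2 stays in the response.** Constrain the baseline means to be equal across arms and include strata-by-visit terms, so that the adjustment acts on the change.

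The models in SAP 3.8, 3.9 and 3.11 that are tied to the primary one should say which baseline value they use.

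The cost is SAP wording and one or two degrees of freedom for the baseline terms. It needs no new data, visits or patients. If baseline and change prove uncorrelated, nothing is gained and those degrees of freedom are the only loss.

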	
through Visit 4 and pulmonary exacerbation rate from Visit 2 through Visit 4
 
Laboratory Measures of Inflammation:
 
 ▪ Difference between treatment groups in the 24-week change from baseline in fecal calprotectin ▪ Difference between treatment groups in the 24-week change from baseline in neutrophil counts, platelet count, and high-sensitivity C-Reactive Protein (hs-CRP) 
Safety:
 
 ▪ Incidence of adverse events (AE) ▪ Changes in safety labs
PLANNED INTERIM ANALYSIS	
When approximately 50% of subjects have completed the study through Visit 4 (Week 24), an interim analysis will be conducted by an independent data monitoring committee (DMC). A priori interim stopping rules for futility and efficacy with respect to the primary endpoint are outlined in the DMC Charter. Serious adverse events (SAE) will be monitored by medical monitors on an ongoing basis throughout the study.

STATISTICS Primary Analysis Plan	
A modified intent to treat (m-ITT) analysis will be used for the primary analysis, including all subjects who were randomized and received at least one dose of study drug.
 
The primary endpoint is the difference between treatment groups of the change in weight-for-age z-score from Visit 2 to Visit 4 (Week 24). A linear mixed effects model will be utilized to incorporate the Visit 3 (Week 12) weight-for-age z-score measurement and the model will adjust for randomization strata: sex, baseline age (< 6 years, ≥ 6 years), baseline weight-for-age z-score (< -0.52, ≥ -0.52) and historical fecal elastase (<200 µg/g, ≥200 µg/g, unavailable). The estimated treatment effect and corresponding 95% confidence interval will be reported and p-values will be evaluated assuming a two-sided 0.05 level of significance.

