15.8 Interim Analysis

An independent DMC will be appointed by the Cystic Fibrosis Foundation DSMB to monitor enrollment, study conduct, efficacy and safety at specified time points and throughout the study

[figure not shown]
as needed. *A priori* stopping rules for efficacy, safety and futility with respect to the primary endpoint will be formalized in conjunction with the DMC and will be put in place prior to initiating the study. One formal interim review will be conducted when approximately 25 subjects have completed the study. Details of these pre-defined stopping rules are specified in the DMC charter.

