1.2 Interim Data Monitoring Committee Reviews

Oversight for this trial is provided by a Data Monitoring Committee (DMC) with members from the Cystic Fibrosis Foundation Therapeutics (CFFT) Data Safety Monitoring Board (DSMB). Abbreviated data summaries are provided to the DMC in periodic interim safety reports, and one more comprehensive interim report.

The purpose of the interim reviews is to monitor enrollment and feasibility, as well as patient safety. The abbreviated safety reports will include a summary of screening, enrollment metrics, baseline characteristics, participant withdrawals and study drug discontinuation, drug compliance (for completed participants), protocol violations, and AEs and SAEs tabulated by treatment group.

The comprehensive interim report expands on the contents of the abbreviated safety reports to include efficacy summaries. The emphasis of the comprehensive report is primarily on safety; however, formal group sequential monitoring of the primary endpoint will be conducted. Please note that informal comparisons of the data between treatment arms must be carefully interpreted in this report given that complete follow up data is not available for all participants.

2. Report Generation

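### The final primary test uses the full two-sided 0.05 although a formal interim look may stop for efficacy; the final nominal level for the two-look design is not stated

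*SAP*

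**What the plan says.** **Interim look.** The synopsis (Planned Interim Analysis) says that a priori "interim stopping rules for futility and efficacy with respect to the primary endpoint are outlined in the DMC Charter". Protocol 15.8 says that "stopping rules for efficacy, safety and futility with respect to the primary endpoint will be formalized in conjunction with the DMC" and refers to the charter for details. SAP 1.2 describes the comprehensive interim report as mainly about safety, but adds that "formal group sequential monitoring of the primary endpoint will be conducted".

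**Timing.** Synopsis: "When approximately 50% of subjects have completed the study through Visit 4 (Week 24), an interim analysis will be conducted". Protocol 15.8: "One formal interim review will be conducted when approximately 25 subjects have completed the study".

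**Final test.** SAP 3.4: "The model-based p-value for the Visit 4 (Week 24) treatment difference will be evaluated against a two-sided 0.05 level of significance", with 95% confidence intervals. Protocol 15.3: "The p-value will be evaluated against a two-sided 0.05 level of significance". Synopsis (Primary Analysis Plan): "p-values will be evaluated assuming a two-sided 0.05 level of significance".

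**What is left to the charter.** The stopping rules (synopsis, protocol 15.8) and the timing and content of the interim reviews (protocol 14). No section sends the final significance level there, gives a spending function, says whether futility is binding, or says that 0.05 is the overall level across both looks.

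**The concern.** An interim look with an efficacy rule gives the trial a second chance to reject the null hypothesis. If the final analysis then uses the whole 0.05, the two chances together exceed 0.05 unless something else, such as a binding futility rule, takes probability away. SAP 3.4 attaches 0.05 to the p-value of one named comparison at Week 24, so it reads as the nominal threshold of the final test and not as an overall level.

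At stake is which threshold and which interval decide the primary claim. If the charter sets a different final level, using it would depart from the SAP text and need justification under SAP 2.2. If the charter sets none, overall type I error is not held at 0.05 with non-binding futility. Either is best settled in writing before unblinding.

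**Working it through.** **Inputs.** SD 0.4, difference 0.36, 54 analysable and 60 enrolled (protocol 15.9); equal allocation (protocol 8.1); final two-sided 0.05 (SAP 3.4). The information fraction t is taken as 25/60 = 0.417, 25/54 = 0.463, 0.50, and 30/54 = 0.556 (half of 60 enrolled against 54 analysable). The boundaries are assumptions.

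**1. The plan's own figure.** Drift = 0.36 / (0.4 × √(2/27)) = 0.36 / 0.1089 = 3.307. A two-sample t-test with 27 per arm (52 df) at a single-look 0.05 has power 90.06%; the normal approximation gives 91.1%. Also 54 / 0.90 = 60. The stated 90% is thus the single-look figure.

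**2. Direction of the error, futility non-binding.** Let Z1 and Z2 be the interim and final statistics, with correlation √t under the null, and c1 the interim efficacy boundary.

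Overall alpha = P(|Z1| ≥ c1) + P(|Z1| < c1, |Z2| ≥ 1.960) = 0.05 + P(|Z1| ≥ c1, |Z2| < 1.960).

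The last term is positive for every finite c1, so any boundary that spends alpha takes the total above 0.05.

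**3. Size.** Overall alpha with the final test at 0.05 / final two-sided level that restores 0.05, by numerical integration:

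| Assumed interim rule | t = 0.417 | t = 0.463 | t = 0.50 | t = 0.556 |
|---|---|---|---|---|
| p<0.001 | 0.05033 / 0.04966 | 0.05027 / 0.04973 | 0.05022 / 0.04978 | 0.05016 / 0.04984 |
| Lan-DeMets O'Brien-Fleming, 0.025 per tail | 0.05035 / 0.04965 | 0.05065 / 0.04934 | 0.05099 / 0.04900 | 0.05165 / 0.04831 |
| Same function, spending two-sided 0.05 | 0.05098 / 0.04901 | 0.05158 / 0.04839 | 0.05216 / 0.04778 | 0.05318 / 0.04668 |
| Classical O'Brien-Fleming | 0.05093 / 0.04906 | 0.05146 / 0.04851 | 0.05196 / 0.04799 | 0.05278 / 0.04711 |

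For example, classical O'Brien-Fleming at t = 0.50 has c1 = 2.797, so P(|Z1| ≥ c1) = 0.00517. Of this, 0.00196 belongs to trials that would not have rejected at the end, which gives 0.05196.

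**4. Small-sample check.** Simulated two-sample t-tests (27 per arm, looks at 25 or 27 completers, 4 million trials, Monte Carlo SE 0.0001), run for the first three rules in the table, give 0.0504 to 0.0526, against 0.0500 to 0.0501 with no interim look.

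**5. If futility binds.** With an assumed binding stop at Z1 < 0, the same rules and looks give a two-sided total of 0.0256 to 0.0309. The excess then disappears.

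**6. Effect on the final test.** Difference needed = critical value × 0.4 × √(2/27). At 1.960 it is 0.213; at the largest adjusted value, 1.989, it is 0.217. Two-look power for 0.36 at the adjusted levels (normal approximation) is 90.9 to 91.1% for t up to 0.50 and 90.8% at worst at t = 0.556, against 91.1% single-look. On the t basis the simulation gives 89.8 to 90.1%, against 90.0 to 90.1%.

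**The case against.** The strongest reply is that a formal group sequential design normally fixes both the interim and the final critical values, that its 0.05 is by convention an overall level, and that the boundary is properly kept in a charter approved before the study starts. Protocol 15.8 is part of the analysis plan, so SAP silence on the boundary changes nothing. This stands to a degree: the charter may already hold an adjusted final level, and the documents do not show that type I error is uncontrolled. It does not remove the gap. SAP 3.4 compares the final p-value directly with 0.05 and makes no cross-reference, so a reader who follows the text would not apply an adjusted level.

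It is also fair to say that the excess depends on two things the documents do not give, the boundary and the futility status. Step 5 shows that even its sign depends on the second.

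A reader might infer three stronger points, none of which the documents support:

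- **Demonstrated inflation.** The two statements do not fit together as written, but the actual error rate cannot be known without the charter.
- **Serious inflation.** A Pocock-type rule would give about 0.067 to 0.069, but nothing in the documents says that one is used.
- **An underpowered trial.** The 90% is a single-look figure, but under conservative boundaries an interim look hardly changes it.

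**Conclusion.** The point holds as a minor defect of specification. Read literally and with non-binding futility, the plan's final threshold and 95% interval do not go with a two-look design that can stop for efficacy. Overall two-sided type I error would be about 0.050 to 0.053, and only a final p-value between about 0.047 and 0.050 could change the conclusion. That size assumes an interim p<0.001 or O'Brien-Fleming type rule and an information fraction of 0.42 to 0.56. The documents confirm neither the rule nor the futility status. Confidence is high on the textual gap and the direction under non-binding futility, and low on the actual size.

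The interim timing (about 50% of subjects against about 25 completers) is an editorial mismatch. Both figures are approximate, and the conclusion is the same under either.

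**What to change.** In SAP 3.4, protocol 15.3 and the synopsis, replace the final-test sentence with wording such as:

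*The overall two-sided type I error across the interim and final analyses is 0.05. The final test will use the two-sided nominal level that, with the efficacy boundary in the DMC Charter and the information fraction observed at the interim look, holds the overall level at 0.05. No credit is taken for futility stopping unless the rule is stated to be binding. The final confidence interval will be reported at the matching level.*

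State in the SAP the boundary and whether futility binds. If the charter already fixes the final level, copy it into the SAP. If efficacy stopping is not intended, remove it from the synopsis and protocol 15.8, adjust SAP 1.2 to match, and keep 0.05. In the same edit, reconcile the interim timing in the synopsis and protocol 15.8.

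The cost is a wording change in the SAP and a protocol clarification. The downside is a slightly stricter final threshold, costing about 0.2 points of power under conservative boundaries (0.3 at worst, at t = 0.556). No change in sample size is needed.
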